10.3.3. Solicited events

a. Solicited administration site events

The following administration site events will be solicited for maternal participants:

Table 25 Solicited administration site events

All age groups
Pain
Redness
Swelling

b. Solicited systemic events

The following systemic events will be solicited for maternal participants:

Table 26 Solicited systemic events

Adult
Fatigue
Fever
Nausea
Vomiting
Diarrhea
Abdominal pain
Headache

Note: maternal participants will be instructed to measure and record the temperature by an age-appropriate route (preferably oral) at least once each day, at approximately the same time each day. If additional temperature measurements are taken at other times of the day, maternal participants will be instructed to record the highest temperature in the electronic Participant Diary (eDiary).

10.3.4. Unsolicited adverse events (AEs)

An unsolicited AE is an AE that was not included in a list of solicited events using a Participant Diary. Unsolicited events must have been spontaneously communicated by a maternal participant who has signed the informed consent/assent. Unsolicited AEs include both serious and non-serious AEs.

Potential unsolicited AEs may be medically attended (i.e., symptoms or illnesses requiring a hospitalization, or an emergency room visit, or visit to/by a health care provider). The maternal participants will be instructed to contact the site as soon as possible to report medically attended event(s), as well as any events that, though not medically attended, are of participant's concern. Detailed information about reported unsolicited AEs will be collected by qualified site personnel and documented in the participant's records.

Unsolicited AEs that are not medically attended or perceived as a concern by the maternal participant will be collected during an interview with the maternal participants and by review of available medical records at the next visit/contact.

10.3.5. Adverse events of special interest (AESIs)

AESIs include:

- **Worsening of pre-existing medical conditions and/or obstetric complications** as defined in section 8.2.1.2.
- The following **pregnancy-related AESIs** (collected as AESI if developed after study intervention administration and were not pre-existing):
 - Maternal death
 - Hypertensive disorders of pregnancy (gestational hypertension, pre-eclampsia, pre-eclampsia with severe features including eclampsia)
 - Fetal growth restriction
 - Gestational diabetes mellitus
 - Pathways to preterm birth (premature preterm rupture of membranes, preterm labor, provider-initiated preterm birth), and
 - Chorioamnionitis.
- The following **neonatal AESIs**:
 - Small for gestational age
 - Low birth weight including very low and extremely low birth weight (<2500 g, <1500g, <1000g)
 - Congenital anomalies (major external structural defects, internal structural defects, functional defects)
 - Neonatal death (in an extremely preterm birth [22<GA<28 weeks], in a preterm live birth [28<GA<37 weeks], or in a term live birth), and preterm birth.

Refer to Section 8.3.4 for additional information about categorizing and reporting congenital anomalies.

When there is enough evidence to make any of the above diagnoses, the AE must be reported as AESI. Symptoms, signs or conditions which might (or might not) lead to one of the above diagnoses, should be recorded and reported as AEs but not as AESI until the

final or definitive diagnosis has been made, and alternative diagnoses eliminated or shown to be less likely.

Note: AESIs experienced by an infant born to the exposed mother will be reported (if become known to the site staff), even if the re-consent for infant participants is not provided.

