4.2.3. Randomization ratio

A 2:1 randomization ratio was chosen to permit efficient evaluation of vaccine safety, reactogenicity and immunogenicity without compromising statistical rigor. Ratios greater than 1:1 for vaccinated vs. placebo recipients increase the likelihood that reported events may occur among vaccine recipients. It is possible that a higher number of reported events among vaccine recipients may be attributed to the greater randomization ratio, the vaccine itself, or due to chance. GSK plans to mitigate the potential risk associated with unbalanced randomization by: a) improving standardization of reporting of pre-defined pregnancy-related and neonatal AESI using Global Alignment of Immunization Safety Assessment in pregnancy [GAIA] definitions; b) referring to the background rates for events available in the literature in the epidemiological study [EPI-RSV-008, 2020] and observational natural history studies [EPI-RSV-015, 2019; EPI-RSV-015, 2020]; and c) establishing processes for continuous review of safety data by the SRT and IDMC.

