 - Gestational diabetes, well-controlled on medications (with or without diet or exercise): i.e. when normoglycemia is maintained (fasting or preprandial blood glucose values <95 mg/dL [5.3 mmol/L], and/or postprandial blood glucose concentration <140 mg/dL [7.8 mmol/L] at 1 hour and/or postprandial blood glucose concentration: <120 mg/dL [6.7 mmol/L] at 2 hours).
 - Gestational hypertension, well-controlled on diet or medications below 160/110 mmHg.
 - Pre-eclampsia without severe features (i.e. eclampsia, severe hypertension [$>160/110$ mmHg], organ dysfunction, unstable or complicated by Hemolysis, Elevated Liver enzymes, and Low Platelets [HELLP] syndrome).
 - Fetal Growth Restriction in singleton pregnancies, with normal umbilical artery (UA) Doppler and estimated fetal weight 3 to 10th percentile for gestational age.
 - History of threatened preterm labor in the current pregnancy, with no cervical dilation greater than 2 cm or effacement exceeding 50%, and/or no progressive change in cervical dilation or effacement detected by serial examinations, when maternal participant is asymptomatic (i.e. no vaginal bleeding or uterine contractions or amniotic fluid loss).
 - Uncomplicated twin gestation.
- Pregnant females at 24^{0/7} to 36^{0/7} weeks of gestation at the time of study intervention administration (Day 1), as established by:
 - Last menstrual period (LMP) date corroborated by first or second trimester ultrasound examination (U/S) (i.e. at or before 28 weeks of gestation).
 - first or second trimester U/S only, if LMP is unknown/uncertain.
 - Certain LMP, corroborated by an U/S performed after 28 weeks of gestation is also acceptable.

Notes: If pregnancy resulted from assisted reproductive technologies, LMP date may be replaced by intrauterine insemination (IUI) or embryo-transfer (ET) date. Refer to Section 10.8 for guidance on gestational age assessment.

The level of diagnostic certainty of the gestational age should be established by using the GAIA gestation age assessment tool (Section 10.8).

- Participants who are willing to provide cord blood.

- Willing to have their offspring followed-up after delivery for a period of 12 months.
- Participants who do not plan to give their offspring for adoption or place the child in care.

Note that women whose pregnancies resulted from assisted reproductive technologies may be enrolled if they meet all inclusion criteria and none of the exclusion criteria.

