4. STATISTICAL ANALYSES

4.1. General Considerations

Unless otherwise specified, reactogenicity analysis will be performed on Solicited Safety Set for maternal participants, and other safety analyses will be performed on Exposed Sets for both maternal and infant participants.

In general, Immunogenicity analysis will be performed on the Per Protocol set. If, in any study group and at any timepoint, the percentage of exposed participants with immunogenicity results excluded from the Per Protocol set is 5% or more, a second analysis based on the Full Analysis Set will be performed to complement the Per Protocol analysis for primary and secondary immunogenicity analysis.

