	
Number and percentage of maternal participants reporting pregnancy-related AESIs * and worsening of pre-existing medical conditions and/or obstetric complications from Day 1 up to 42 days post-delivery. * These include maternal death, hypertensive disorders of pregnancy (gestational hypertension, pre-eclampsia, pre-eclampsia with severe features including eclampsia), fetal growth restriction, gestational diabetes mellitus, pathways to preterm birth (premature preterm rupture of membranes, preterm labor, provider-initiated preterm birth) and chorioamnionitis.
	
The number and percentage of maternal participants reporting each pregnancy-related AESI and worsening of pre-existing medical conditions and/or obstetric complications from Day 1 up to 42 days post-delivery will be tabulated with its exact 95% CI by group.
 
By participant listings of pregnancy-related AESIs and worsening of pre-existing medical conditions and/or obstetric complications will be prepared.

CONFIDENTIAL

	Primary Safety Endpoints	Statistical Analysis Methods
Infant participants	
Number and percentage of infant participants reporting neonatal / infant AESIs * from birth up to 42 days post-birth.
 
* These include small for gestational age, low birth weight including very low and extremely low birth weight (<2500 g, <1500g, <1000g), congenital anomalies (major external structural defects, internal structural defects, functional defects), neonatal death (in an extremely preterm birth [22<GA<28 weeks], in a preterm live birth [28<GA<37 weeks], or in a term live birth) and preterm birth.
	
The number and percentage of infant participants reporting each neonatal / infant AESI from birth up to 42 days post-birth will be tabulated with its exact 95% CI by group.
 
By participant listings of neonatal / infant AESIs will be prepared.

	
Number and percentage of infant participants reporting SAE, (S)AEs leading to study withdrawal, and MAEs from birth up to 42 days post-birth.
	
The number and percentage of infant participants reporting:
 
 • at least one SAE • at least one (S)AE leading to study withdrawal • at least one MAE 
from Day 1 up to 42 days post-birth with exact 95% CIs will be tabulated by group and by MedDRA preferred term.
 
By participant listings of SAEs, (S)AEs leading to study withdrawal and MAEs will be prepared.

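### New-onset gestational diabetes, fetal growth restriction and same-subcategory hypertensive disorders are shown as a percentage of all dosed women, including women enrolled because they already had the condition

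*Protocol*

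**What the plan says.** Protocol 10.3.5 lists the pregnancy-related AESIs, including hypertensive disorders of pregnancy, fetal growth restriction and gestational diabetes, and restricts them to events "collected as AESI if developed after study intervention administration and were not pre-existing". Deterioration of a condition already present is a separate AESI, worsening, defined in Protocol 8.2.1.2.

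Protocol 5.1.1 makes several of the same conditions grounds for entry in adults. One is gestational diabetes controlled on medication. Another is "Gestational hypertension, well-controlled on diet or medications below 160/110 mmHg". Pre-eclampsia qualifies if it lacks severe features, and so does "Fetal Growth Restriction in singleton pregnancies, with normal umbilical artery (UA) Doppler". Adolescents of 15 to 17 years enter as healthy.

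SAP 4.2.1.1 counts, within each group, the women "reporting each pregnancy-related AESI and worsening of pre-existing medical conditions and/or obstetric complications from Day 1 up to 42 days post-delivery", and gives each count as a percentage with exact 95% limits. Apart from reactogenicity, SAP 4.1 says that "other safety analyses will be performed on Exposed Sets for both maternal and infant participants". SAP 3.1 defines the maternal Exposed Set as all women who received a dose, with no restriction to women free of a given condition. Neither document sets an at-risk denominator for any AESI.

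Minimization (Protocol 6.3.3) and the listed subgroup (SAP 4.6.2) use the presence or absence of any obstetric complication, not the particular condition. Maternal safety is also summarized by age, under 18 against 18 and over.

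**The concern.** A woman enrolled with gestational diabetes cannot contribute a new-onset gestational diabetes event, yet she stays in the denominator. The same holds for fetal growth restriction, and for a hypertensive disorder of the subcategory she already has.

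The resulting percentage is a valid proportion of dosed women with a new event, but it understates incidence among women who could have one, and its upper confidence limit is too low for that purpose. These are primary safety endpoints in a trial whose enrolment was stopped over a safety signal elsewhere in the programme, so a limit that looks tighter than the data support matters.

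The age summaries have the problem by design. Healthy adolescents are nearly all at risk of these events, while an unknown share of adults is not.

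**Working it through.** **Inputs.** Planned group sizes of 252 and 126 (Protocol 4.1, Table 5); exact Clopper-Pearson 95% limits (SAP 4.1.1); 10 events as an example, because it is a row of the plan's own precision table. The share q with the condition at entry is not in the documents and is assumed to lie between 10% and 50%.

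**Reproducing the plan (Protocol 9.2.1; SAP 5.1).** The chance of at least one event is 1 − (1 − p)^252. At p = 0.5%, 1% and 1.5% this gives 71.7%, 92.1% and 97.8%, against the stated 72%, 92% and 98%. The exact interval for 10 of 252 is 1.9% to 7.2%, and the upper limit for 0 of 252 is 1.5%. Both match the plan's table.

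**Dilution.** If r is the rate among women at risk, the expected number of events is r × N × (1 − q). Dividing by N gives a displayed rate of r × (1 − q). The table recomputes the same quantities on n = 252 × (1 − q).

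| q (assumed) | Women at risk | 10 events: % (exact 95% CI) | Upper limit, 0 events | Chance of ≥1 event at r = 1% |
|---|---|---|---|---|
| All exposed, as planned | 252 | 4.0 (1.9 to 7.2) | 1.5% | 92% |
| 10% | 227 | 4.4 (2.1 to 8.0) | 1.6% | 90% |
| 30% | 176 | 5.7 (2.8 to 10.2) | 2.1% | 83% |
| 50% | 126 | 7.9 (3.9 to 14.1) | 2.9% | 72% |

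Absolute differences between groups shrink by the same factor. A 5.0-point difference among women at risk shows as 4.5, 3.5 or 2.5 points at q = 10%, 30% and 50%.

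**Between groups.** If q is the same in both groups, (1 − q) cancels from the rate ratio. Chance differences in q remain. Under simple randomization the SD of the difference is √[q(1 − q)(1/252 + 1/126)], so the 95% range is about ±6.4, ±9.8 and ±10.7 percentage points at q = 10%, 30% and 50%. With no vaccine effect, and apart from chance in the events themselves, this alone moves the all-exposed rate ratio over about 0.93 to 1.08, 0.87 to 1.16 and 0.81 to 1.25.

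**Between ages.** With equal incidence among women at risk, and adolescents all at risk, the adult percentage is (1 − q) times the adolescent one: 0.9 at q = 10% and 0.5 at q = 50%, with q now the share among adults.

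**The case against.** The strongest defence is that the all-exposed percentage is a legitimate cumulative proportion, the analysis is descriptive, and randomization makes q equal between groups in expectation. That stands. A reader might infer that the vaccine comparison is biased. It is not: unequal q between groups is chance variation, which adds noise.

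A second defence is that the at-risk rate may be recoverable. SAP 6.1.2.2 summarizes past history and current conditions by MedDRA term, and AESI listings are planned. This stands only in part. That sentence does not say the summary is by group, it does not separate current from past conditions, and it gives no at-risk rate or interval. The obstetric-complication subgroup in SAP 4.6.2 pools all conditions, and the detailed safety text there names only maternal age and gestational age at birth.

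Three further readings go beyond the documents:

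- **That no woman with a hypertensive disorder at entry can have a hypertensive AESI.** The category has three subcategories (Protocol Section 3, Table 4, footnote 1). A woman enrolled with gestational hypertension may later meet the definition of pre-eclampsia. Neither document says whether that is a new AESI or worsening.
- **That overall worsening is diluted in the same way.** Every adult has HIV and/or an obstetric complication or risk factor. Women with no qualifying condition are the healthy adolescents, planned at 18 or more of 378 (18/378 = 4.8%), so overall worsening is diluted by about 5% at that share. The mirror problem matters only where worsening is split by condition.
- **That the percentages cannot be set against background rates.** Protocol 4.2.3 mentions "referring to the background rates for events available in the literature" as one mitigation of the 2:1 allocation. The denominators of those rates are not in the documents, so comparability cannot be judged either way.

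**Conclusion.** The point holds for gestational diabetes, fetal growth restriction and hypertensive disorders of the subcategory present at entry. Followed as written, the plan understates incidence among women at risk by the factor (1 − q), together with its upper limits. At q = 10% the effect is slight. At q = 50% the rate among women at risk is twice the displayed rate, and the zero-event upper limit is 2.9%, not 1.5%.

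The size rests on the assumed range for q, which would differ by condition, and on the planned 252 and 126. Enrolment was stopped and the documents do not give the number reached. Fewer women would widen every interval and the chance imbalance, but would leave the factor (1 − q) unchanged. The imbalance figures assume simple randomization. Minimization on any-complication status does not control the individual condition.

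The age summaries are affected by design, although with so few adolescents planned they will be imprecise in any case.

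**What to change.** Keep the all-exposed rows. In SAP 4.2.1.1 and 4.3.1.1:

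1. For each of these AESIs, add a row by group among exposed women without that condition at Day 1, with an exact 95% CI.
2. Show the Day 1 count of each condition by group.
3. Where worsening is tabulated by condition, add a row among women who have that condition.
4. State whether progression within hypertensive disorders, for example from gestational hypertension to pre-eclampsia, counts as a new AESI or as worsening.

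Pre-existing conditions are already recorded (Protocol 8.2.1.3), so no new data are needed. No hypothesis is tested, so no test or sample size changes. The cost is a few more table rows, with smaller denominators and wider intervals.

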10.3.6. Clinical laboratory parameters and other abnormal assessments qualifying as AEs or SAEs

In the absence of a diagnosis, abnormal laboratory findings assessments (e.g. clinical chemistry, hematology, urinalysis) or other abnormal results the investigator considers clinically significant will be recorded as an AE or SAE, if they meet the definition of an AE or SAE (refer to the Sections [10.3.1](#) and [10.3.2](#)).

The investigator must exercise his or her medical and scientific judgment in deciding whether an abnormal laboratory finding, or other abnormal assessment is clinically significant.

10.3.7. Events or outcomes not qualifying as AEs or SAEs

10.3.7.1. Subsequent Pregnancy

All maternal participants will be in the second or third trimester of pregnancy at enrollment and are expected to deliver while participating in the study.

Maternal participants who become pregnant again after administration of the study intervention may continue the study at the discretion of the investigator.

While subsequent pregnancy itself is not considered an AE or SAE, any abnormal subsequent pregnancy outcome or complication or elective termination of a subsequent pregnancy for medical reasons will be recorded and reported as an SAE. Please refer to the Section [10.3.2](#) for definition of SAE.

10.3.8. Recording and follow-up of AEs, SAEs, AESIs and subsequent pregnancies

The maternal participants/infant participants' parent(s)/LAR(s) will be instructed to contact the investigator immediately should the maternal or infant participants experience any signs or symptoms the maternal participants/infant participants' parent(s)/LAR(s) perceive as serious.

When an AE/SAE occurs, it is the investigator's responsibility to review all documentation (e.g. hospital progress notes, laboratory and diagnostics reports) related to the event. The investigator will then record all relevant information regarding an AE/SAE on the eCRF. The investigator may not send photocopies of the participant's medical records to GSK instead of appropriately completing the eCRF.

There may be instances when copies of medical records for certain cases are requested by GSK. In this case, all participant identifiers will be blinded on copies of the medical records prior to submission to GSK.

The investigator will attempt to establish a diagnosis pertaining to the event, based on signs, symptoms, and/or other clinical information. In such cases, the diagnosis should be documented as the AE/SAE instead of individual signs/symptoms.

An Electronic Diary (eDiary), hereafter referred to as Participant Diary, will be used in this study to capture solicited administration site or systemic events for maternal participants. The maternal participant should be trained on how and when to complete the Participant Diary.

Anyone who measures administration site or systemic events and who will record the event in the Participant Diary should be trained on using the Diary. This training must be documented in the maternal participant's source record. If any individual other than the maternal participant is making entries in the Participant Diary, their identity must be documented in the Participant Diary/maternal participant's source record.

Refer to the SPM for more information regarding the use of eDiary.

Note: SAEs and/or AESIs experienced by an infant born to the exposed mother will be reported (if become known to the site staff), even if the re-consent for infant participants is not provided.

10.3.8.1. Time period for collecting and recording AEs, SAEs, AESIs and subsequent pregnancies

For time period and frequency for collecting AE, SAE and other safety information, refer to Section [8.3.1](#).

All solicited events that occur during 7 days following administration of the dose of study intervention (Day 1 to Day 7) must be recorded into the eDiary, irrespective of intensity or whether or not they are considered related to the study intervention.

All other AEs should be recorded into the appropriate section of the eCRF, irrespective of their intensity or whether or not they are considered related to the study intervention.

10.3.8.2. Follow-up of AEs, SAEs, AESIs, subsequent pregnancies or any other events of interest

10.3.8.2.1. Follow-up during the study

After the initial AE/SAE/AESI/subsequent pregnancy or any other event of interest, the investigator is required to proactively follow each participant at subsequent visits/contacts.

All SAEs and AESIs (serious or non-serious as defined in the Section 10.3.5), will be followed until the event is resolved, stabilized, otherwise explained, or the participant is lost to follow-up.

Non-serious MAEs must be followed until recovered / resolved, or until the participant's last study visit, or until the participant is lost to follow-up.

Other non-serious AEs (maternal participants) must be followed until they are resolved, stabilized or until the participant is lost to follow-up.

AEs/AESIs documented at a previous visit/contact and defined as not recovered/not resolved or recovering/resolving will be reviewed at subsequent visits/contacts until they are resolved, stabilized or until the participant is lost to follow-up.

If a participant dies during their participation in the study or during a recognized follow-up period, GSK will be provided with any available post-mortem findings, including histopathology.

